4.1.1.2 Clinical Assessments

ACR Response is derived through a combination of reductions from baseline in swollen or tender joint counts as well as improvement from baseline in at least 3 of the other parameters (patient assessment, physician assessment, pain scale, disability/functionality questionnaire, and acute phase reactant [ESR]). This study will evaluate the following three levels of ACR Response:

• ACR20: An ACR20 indicates that 20% improvement is observed in tender and swollen joint counts as well as 20% improvement in at least 3 of the other 5 criteria.

- ACR50: An ACR50 indicates that 50% improvement is observed in tender and swollen joint counts as well as 50% improvement in at least 3 of the other 5 criteria.
- ACR70: An ACR70 indicates that 70% improvement is observed in tender and swollen joint counts as well as 70% improvement in at least 3 of the other 5 criteria.

Each patient will be classified as a yes or a no for whether they meet each of the above ACR Response Criteria at each of the applicable post-baseline time points. Note that the above criteria are nested, such that if a patient is a yes for ACR70 at a given time point, then the patient is also a yes for ACR50 and ACR20 for that same time point.

A patient will be classified as improved on the CDAI depending on the baseline score as follows:

- If the baseline value is greater than 22, a reduction of more than 12 will be classified as improved. Otherwise, the patient is not improved.
- If the baseline value is between 10 and 22 (inclusive) a decrease of more than 6 will classified as improved. Otherwise, the patient is not improved.
- If the baseline value is less than 10, a decrease of more than 1 will be classified as improved. Otherwise the patient is not improved.

A patient will be classified as improved on the DAS28 with a score change of greater than 1.2.

A decrease of at least 0.22 in the HAQ-DI will be classified as improved. Otherwise, the patient is not improved on the HAQ-DI.

4.1.2 Description of Primary Efficacy Variables

The primary efficacy variables for determining clinical response are the response/non-response status at 24 weeks to new or changed anti-TNF α bDMARD therapy for rheumatoid arthritis based on the ACR50 criterion. The primary efficacy variables for determining the predicted response and non-response are Δ TUV_{global[5w]} bucketing.

The co-primary efficacy endpoints of the study are:

- Specificity of $\Delta TUV_{global[5w]}$ bucketing with respect to ACR50 at week 24.
- Sensitivity of $\Delta TUV_{global[5w]}$ bucketing with respect to ACR50 at week 24.

4.1.3 Description of Key Secondary Efficacy Variables

The key secondary efficacy endpoint is:

• NPV of TUV_{global[b]} with respect to ACR50 at week 24.

4.1.4 Description of Secondary Efficacy Variables

The secondary efficacy predictor variables are the findings based on prediction algorithms 1 and 2, as described in Section 4.1.1.

The secondary efficacy response variables are:

- CDAI score at baseline (CDAI_b), 12 (CDAI_{12w}) and 24 weeks (CDAI_{24w})
- ACR Response Criteria (ACR20, ACR50, ACR70) at 12 and 24 weeks
- DAS28 Score at baseline, 12 weeks, and 24 weeks
- Constituent scores of the ACR Response Criteria at baseline, 12 weeks, and 24 weeks, including:
 - o TJC
 - o SJC
 - Patient assessment of global disease activity
 - Rheumatologist assessment of global disease activity
 - Patient assessment of pain
 - Patient assessment of physical function
 - Acute-phase reactant value
- Constituent scores of the CDAI score at baseline, 12 weeks, and 24 weeks, including:
 - o TJC
 - o SJC
 - Patient Global Assessment
 - Physician Global Assessment

The secondary efficacy endpoints are as follows:

- Sensitivity and specificity of ΔTUV_{global[5w]} bucketing with respect to ACR50 at week 12.
- NPV, PPV, and OA of ΔTUV_{global[5w]} bucketing with respect to ACR50 at weeks 12 and 24.
- NPV of TUV_{global[b]} with respect to ACR50 at week 12
- TUV_{global[b]} and response to new anti-TNFα bDMARD therapy defined by the change from baseline (CFB) of CDAI to 12 ± 1 weeks and 24 ± 1 weeks (ΔCDAI_{12w} and ΔCDAI_{24w}, respectively), by the CFB of DAS28 to 12 ± 1 weeks and 24 ± 1 weeks (ΔDAS28_{12w} and ΔDAS28_{24w},

respectively) and by the CFB in each of the ACR Response Criteria components at 12 ± 1 weeks and at 24 ± 1 weeks.

- $\Delta TUV_{global[5w]}$ bucketing and response to new anti-TNF α bDMARD therapy defined by the CFB of CDAI to 12 ± 1 weeks and 24 ± 1 weeks ($\Delta CDAI_{12w}$ and $\Delta CDAI_{24w}$, respectively).
- Concordance of ΔTUV_{global[5w]} bucketing with clinical criteria, including ACR Response Criteria, CDAI, DAS28, and HAQ-DI[©]. Concordance between the predicted response or non-response status and the clinical criteria will be evaluated using NPV, PPV, sensitivity, specificity, and OA.
- Concordance of ΔTUV_{global[12w]} bucketing with clinical criteria, including ACR Response Criteria, CDAI, DAS28, and HAQ-DI[©]. Concordance between the improvement classifications and the clinical criteria will be evaluated using NPV, PPV, sensitivity, specificity, and OA.
- Response to new anti-TNFα bDMARD therapy defined by the CFB of CDAI to 12 ± 1 weeks and 24 ± 1 weeks (ΔCDAI_{12w} and ΔCDAI_{24w}, respectively).
- The correlation of ΔTUV_{global[5w]} bucketing and response to new anti-TNFα bDMARD therapy from baseline to 24 ± 1 weeks defined by the changes from baseline in each of the ACR Response Criteria components.
- Constituent parameters of CDAI_{12w}, CDAI_{24w}, ΔCDAI_{12w}, ΔCDAI_{24w}, ACR Response Criteria at 12 and 24 weeks, including:
 - o TJC
 - o SJC
 - Patient assessment of global disease activity
 - Rheumatologist assessment of global disease activity
 - Patient assessment of pain
 - Patient assessment of physical function
 - Acute-phase reactant value

4.2 Analysis of Efficacy Variables

Efficacy analyses will be conducted on the ITD and PP populations, with the ITD population serving as the primary analysis population.

4.2.1 Analysis of Primary Efficacy Variables

The co-primary efficacy variables will be summarized by reader in a 2 by 2 contingency table displaying the cell frequencies and marginal totals at 24 weeks. The specificity of $\Delta TUV_{global[5w]}$ bucketing and the sensitivity of $\Delta TUV_{global[5w]}$ bucketing will be calculated for each reader. The 95% exact (Clopper-Pearson) confidence intervals will be provided for each of these parameters. Observed significance levels (p-values) for the exact binomial tests of specificity of $\Delta TUV_{global[5w]}$ bucketing greater than 0.8 and sensitivity of

 $\Delta TUV_{global[5w]}$ bucketing greater than 0.65 (see hypotheses specified in Section 1.3 above) will be provided.

Sensitivity and specificity are defined according to the following cross-tabulation:

	Clinical Response			
Predicted Response	Responder	Non-Responder	Total	
Responder	А	В	T1	
Non-Responder	С	D	T ₂	
Total	Тз	T_4	Ν	

Sensitivity = $A/T_{3.}$ Specificity = $D/T_{4.}$

The above 2 by 2 contingency table will also be used to calculate the secondary efficacy endpoints of NPV, PPV, and OA as follows:

 $\begin{aligned} \mathsf{NPV} &= \mathsf{D}/\mathsf{T}_2.\\ \mathsf{PPV} &= \mathsf{A}/\mathsf{T}_1.\\ \mathsf{OA} &= (\mathsf{A} + \mathsf{D})/\mathsf{N}. \end{aligned}$

4.2.2 Analysis of Key Secondary Efficacy Variables

NPV of TUV_{global[b]} will be calculated for each reader. The 95% exact (Clopper-Pearson) confidence intervals will be provided. Observed significance levels (p-values) for the exact binomial tests of NPV of TUV_{global[b]} greater than 0.7 will be provided.

4.2.3 Analysis of Secondary Efficacy Variables

All RA quantitative assessment variables (CDAI, ACR Response Criteria component scores, DAS28 score, and HAQ-DI) will be summarized by computing the mean, standard deviation, number of observations, minimum, median, and maximum for the observed values at each time point and for the change from baseline for values collected after Day 0. The ACR Response Criteria will be summarized with a frequency table of the highest ACR Response level (None, ACR20, ACR50, ACR70) attained by that patient at that time point. That is, a patient who satisfies ACR50 also satisfies ACR20 but will not appear in the frequency count for ACR20.

The qualitative assessments will be summarized in a 2 by 2 contingency table displaying the cell frequencies and marginal totals by reader as shown in section

4.2.1 above. The PPV and NPV of the predicted response will be calculated for each reader, as will the OA. In addition, 95% exact confidence intervals will be provided for each of these parameters. Observed significance levels (p-values) for the exact binomial (Clopper-Pearson) tests of PPV and NPV (see sections 1.3 and 4.2.1 above) will be provided for each reader. These tests will be based on PPV of the predicted response greater than 0.65, and NPV of the predicted response greater than 0.7.

Concordance of improvement classification for: 1) $\Delta TUV_{global[5w]}$ bucketing and 2) $\Delta TUV_{global[12w]}$ bucketing with clinical criteria (ACR Response, CDAI, DAS28, and HAQ-DI) will be analyzed as follows. Note that the concordance of $\Delta TUV_{global[5w]}$ bucketing with ACR50 at 24 weeks is evaluated as co-primaries (sensitivity and specificity). For each of the RA improvement criteria, a cross-classification table will be provided. The PPV, NPV, sensitivity, specificity, and OA will be calculated and 95% exact (Clopper-Pearson) confidence intervals will be provided. Observed significance levels (p-values) for the exact binomial (Clopper-Pearson) tests for sensitivity and specificity will be provided for each reader.

Figures displaying the ΔTUV_{global} by time point (5, 12, and 24 weeks) will be created to display the relationship between ΔTUV_{global} over time with the corresponding clinical response assessment (ACR20/50/70, DAS28, and CDAI) at the given time point.

The Kendall rank correlation between $\Delta TUV_{global[5w]}$ with $\Delta CDAI_{12w}$ and $\Delta CDAI_{24w}$ will be computed and a 95% confidence interval for its value will be computed using Fisher's Z-transformation. Similarly, the Kendall rank correlation between $\Delta TUV_{global[5w]}$ with changes from baseline in DAS28 and in each of the ACR Response Criteria components at weeks 12 and 24 will be computed and a 95% confidence interval for its value will be computed using Fisher's Z-transformation. The marginal distributions of the variables will be characterized with the mean, standard deviation, and the number of data pairs.

The additive effect of either quantitative or qualitative assessment of Tc 99m tilmanocept imaging will be assessed with a generalized linear mixed model with the logit link function. The patient's response status will be used as the response variable. Fixed model terms for the quantitative and qualitative plus quantitative assessments will be used. The quantitative assessment will be based on $\Delta TUV_{global[5w]}$ bucketing. Random terms will be fit for the subject and reader within subject using the variance component model. A table displaying the partial hypothesis tests (Type 3 test) for the fixed effects will be displayed.

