To evaluate the power characteristics of this process with 3 correlated readers where at least the same two of the three readers must reject both null hypotheses above, a simulation study was performed. Correlated binomial random variables were generated using a copula. The hypotheses were tested for each simulated reader using an exact binomial test, and the number of iterations where at least the same two of the three readers rejected both hypotheses was counted. Under the conditions above this procedure has power 0.93 when $\rho = 0.7$ and 0.89 when $\rho = 0.9$.

In Arm 3 of the NAV3-31 study a ratio of 5 non-responders to 1 responder was observed. If this ratio is maintained in NAV3-33 for the $\Delta TUV_{global[5w]}$ with bucketing predictions, a total of 600 patients is needed to achieve the desired power. That is, a total of 500 clinical non-responder patients is expected to be enrolled before reaching the required 100 clinical responders.

Taking into account a 10% dropout rate, the anticipated total sample size for the study is approximately 672 patients (560 clinical non-responders and 112 clinical responders). That is:

- Clinical Non-Responders: 90% completion rate relative to 560 enrolled patients will result in 500 completed patients
- Clinical Responders: 90% completion rate relative to 112 enrolled patients will result in 100 completed patients

Because there is uncertainty about how responding and non-responding patients will enroll, enrollment may continue until at least 560 clinical non-responders and 112 clinical responders are participating in the study. The cumulative enrollment of clinical non-responders and responders will be tracked throughout the study in order to stop enrollment once the required number has been reached for each clinical category. This tracking of clinical response and non-response status will be performed by individuals without knowledge of the TUV data. At the Sponsor's discretion, the week 12 clinical response outcomes may be used to help track enrollment.

If the two co-primary endpoints are achieved (i.e., both null hypotheses are rejected for at least the same 2 out of 3 readers), then the following hypotheses will be tested at one-tailed 0.025 for the key secondary endpoint of NPV of TUV_{global[b]} with respect to ACR50 at week 24:

$$H_{03}: \pi_{\text{NPV}} \le 0.7$$

 $H_{A3}: \pi_{\text{NPV}} > 0.7;$

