Х	Improved	xxx (xxx%)	xxx (xxx%)	xxx (xxx%)	PPV	XXXX
					Confidence Limits	(XXXX, XXXX)
					p-value	X.XXXX
	Not Improved	xxx (xxx%)	xxx (xxx%)	xxx (xxx%)		
					NPV	XXXX
	Total	xxx (xxx%)	xxx (xxx%)	xxx (xxx%)	Confidence Limits	(XXXX, XXXX)
					p-value	X.XXXX
					OA	XXXX
					Confidence Limits	(XXXX, XXXX)

 a p-values for PPV testing Ho: π = 0.65 and for NPV testing Ho: π = 0.7. STATKING Clinical Services (DD-MMM-YYYY) Source Program: xxxxxx.sas

Within each part, the above will be displayed for each reader. This format repeats for Part 2 (ACR50), Part 3 (ACR70), Part 4 (CDAI), Part 5 (DAS28), and Part 6 (HAQ-DI). Full table format repeats for PP population (table 22) and for tables 23 – 28.

Table 29. Kendall Rank Correlation of ΔTUV, ΔCDAI, ΔACR Response Criteria Components, and ΔDAS28 with ΔTUV at 5 Weeks Navidea Biopharmaceuticals - Study No. NAV3-33 ITD Population (N=xxx)

Part 1 of 3: Reader x

	Component		Kendall	95% Confidence			Standard
Measure ^a	Parameter	Time Point	Correlation ^b	Limits ^c	n	Mean	Deviation
Δ TUV		5 Weeks			XXX	XXXXXX	XXXXXX
Δ TUV		12 Weeks	X.XXX	(x.xxx, x.xxx)	XXX	XXXXXX	XXXXXX
		24 Weeks	x.xxx	(x.xxx, x.xxx)	XXX	XXXXXX	XXXXXX
Δ CDAI	Overall	5 Weeks	X.XXX	(x.xxx, x.xxx)	XXX	XXXXXX	XXXXXX
		12 Weeks	X.XXX	(x.xxx, x.xxx)	XXX	XXXXXX	XXXXXX
		24 Weeks	X.XXX	(x.xxx, x.xxx)	XXX	XXXXXX	XXXXXX
Δ CDAI	XXXXXXXX	5 Weeks	X.XXX	(x.xxx, x.xxx)	XXX	XXXXXX	XXXXXX
		12 Weeks	X.XXX	(x.xxx, x.xxx)	XXX	XXXXXX	XXXXXX
		24 Weeks	X.XXX	(x.xxx, x.xxx)	XXX	XXXXXX	XXXXXX
Δ ACR	XXXXXXXX	5 Weeks	X.XXX	(x.xxx, x.xxx)	XXX	XXXXXX	XXXXXX
		12 Weeks	X.XXX	(x.xxx, x.xxx)	XXX	XXXXXX	XXXXXX
		24 Weeks	x.xxx	(x.xxx, x.xxx)	XXX	XXXXXX	XXXXXX
Δ DAS28		5 Weeks	X.XXX	(x.xxx, x.xxx)	XXX	XXXXXX	XXXXXX
		12 Weeks	x.xxx	(x.xxx, x.xxx)	XXX	XXXXXX	XXXXXX
		24 Weeks	x.xxx	(x.xxx, x.xxx)	XXX	XXXXXX	XXXXXX

^a Change in ACR will be evaluated through the following components of the ACR Response Criteria: swollen joint count, tender joint count, patient assessment, physician assessment, pain scale, disability/functionality questionnaire, and acute phase reactant (ESR).

 $^{
m b}$ Kendall rank correlation between Δ TUV at 5 weeks and the indicated measurement and time point.

 $^{\circ}$ Confidence limits calculated using Fisher's Z-transformation.

STATKING Clinical Services (DD-MMM-YYYY)

Source Program: xxxxxx.sas

Table format is repeated for each reader. Entire table (all parts) is repeated for the PP population (table 30).

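### The qualitative reads are tested against fixed PPV and NPV nulls that have no source for PPV and depend on the response rate: at the expected 5:1 ratio an uninformative read passes the NPV test.

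*SAP*

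**What the plan says.** SAP 4.2.3 puts the qualitative assessments in a 2 by 2 table for each reader and asks for PPV, NPV and OA with exact intervals. It then adds exact binomial "tests of PPV and NPV (see sections 1.3 and 4.2.1 above) will be provided for each reader". The nulls are explicit: "PPV of the predicted response greater than 0.65" and "NPV of the predicted response greater than 0.7".

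The Table 21 footnote in Appendix B repeats them: "p-values for PPV testing Ho: π = 0.65 and for NPV testing Ho: π = 0.7". Within the table, "This format repeats for Part 2 (ACR50), Part 3 (ACR70), Part 4 (CDAI), Part 5 (DAS28), and Part 6 (HAQ-DI"), and the whole shell is reused for Tables 22-28. Tables 25-28 are the qualitative-plus-quantitative read. The text of 4.2.3 mentions only the qualitative assessments, so the tests reach the combined read through the shell alone. The shell prints PPV, NPV and OA, with no line for sensitivity or specificity.

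The cited sections say the following.

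- Section 1.3 has three hypotheses: specificity against 0.8, sensitivity against 0.65, and NPV against 0.7 for baseline TUV_global.
- Section 4.2.1 tests specificity against 0.8 and then sensitivity of the quantitative "bucketing greater than 0.65 (see hypotheses specified in Section 1.3 above) will be provided". PPV appears there only as the formula A/T1.

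For the quantitative algorithm, the next paragraph of 4.2.3 and the Table 11 shell give p-values for sensitivity and specificity. PPV, NPV and OA are shown there with intervals only.

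**The concern.** There are two linked problems. First, the PPV test has no hypothesis behind it in the sections it cites, and the NPV null was set for a different predictor. Second, PPV and NPV depend on the proportion of clinical responders as well as on the read. For a read unrelated to outcome, NPV equals the non-responder proportion, so it exceeds 0.7 whenever fewer than 30% of patients respond. Section 1.3 builds the sample size on a prior arm in which "a ratio of 5 non-responders to 1 responder was observed", which is about 17% responders.

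At stake is how the qualitative objective is reported. A significant NPV p-value could be presented as support for a read that carries no information. A read as accurate as the design assumes for the quantitative algorithm would usually show a non-significant PPV.

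**Working it through.** **Inputs.** All are from SAP 1.3 unless stated: 100 responders and 500 non-responders at 5:1; sensitivity (Se) 0.80 and specificity (Sp) 0.92 as the design values; one-sided 0.025. Section 4.2.3 does not state sidedness, so 0.025 is carried over. The nulls of 0.65 (PPV) and 0.7 (NPV) are from 4.2.3. The cells A, B, C and D are those of the 4.2.1 table.

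**Rule.** For n patients and null p0, reject when the count is at least r, the smallest value with P(X ≥ r | n, p0) ≤ 0.025.

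**Reproducing the plan's own figures.**

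- Specificity: n = 98, r = 87, power 0.908.
- Sensitivity: n = 100, r = 75, power 0.913. Both agree with the stated 90%.
- Baseline NPV, 0.85 against 0.70: n = 89 gives 0.888 and n = 71 gives 0.830, close to the stated 90% and 80%.

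**A read at the design values, 100:500.**

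- A = 0.80 × 100 = 80 and B = 0.08 × 500 = 40, so PPV = 80/120 = 0.667. NPV = 460/480 = 0.958.
- With 120 predicted responders, r = 89 (74.2%). The expected 80/120 gives p = 0.39.
- Probability of passing PPV > 0.65: 0.048 if the 120 is held fixed. It is 0.021 when A ~ Bin(100, 0.80) and B ~ Bin(500, 0.08) both vary, 0.023 with 112:560, and 0.050 at one-sided 0.05.

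**An uninformative read, 100:500.**

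- NPV = 500/600 = 0.833 and PPV = 100/600 = 0.167, however often it predicts response.
- Coin flip: C = 50 and D = 250, so NPV = 250/300. It passes NPV > 0.7 with probability above 0.999.
- Predicting response in 80% of patients: it still passes NPV with probability 0.94.
- In both cases it passes PPV with probability of effectively 0.

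**The same reads on the co-primary measures.** The design read passes sensitivity with probability 0.913 and specificity with probability above 0.999. The coin flip passes either with probability below 0.000001.

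**Dependence on the ratio** (100 responders, both cells varying).

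| Non-responders : responders | Design read: PPV | Passes PPV > 0.65 | Coin flip: NPV | Passes NPV > 0.7 |
|---|---|---|---|---|
| 5:1 | 0.667 | 0.02 | 0.833 | > 0.999 |
| 4:1 | 0.714 | 0.23 | 0.800 | 0.99 |
| 3:1 | 0.769 | 0.77 | 0.750 | 0.25 |
| 2:1 | 0.833 | > 0.99 | 0.667 | about 0 |
| 98:100 | 0.911 | about 1 | 0.495 | 0 |

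Each read has the same sensitivity and specificity in every row. Only the mix of patients changes.

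**The case against.** Several points on the other side stand.

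- A reader might infer that the planned outputs cannot tell a good read from a useless one. The documents do not support that. At 5:1 the coin flip fails PPV with near certainty. At expected counts the planned exact intervals are far apart: PPV 0.575-0.750 against 0.126-0.214, and NPV 0.936-0.974 against 0.786-0.874. The fault is in the p-values taken singly, and nothing says both must be significant.
- A reader might infer that the qualitative or additive objective cannot be met. That is also too strong. PPV, NPV and OA are reported for both kinds of read, a generalized linear mixed model addresses the additive effect, and sensitivity and specificity can be worked out from the displayed 2 by 2 counts.
- A true PPV of 0.667 seldom rejects a null of 0.65 because it lies only just above it. That is correct test behaviour. At 5:1 with sensitivity 0.80, a read with specificity 0.95 passes with probability 0.70, and one with 0.96 passes with probability 0.94.
- The 5:1 ratio is conditional. The protocol allows 198 to 672 evaluable subjects, and response rates for the other criteria in Tables 21-28 are not given. The values 0.80 and 0.92 are assumed for the quantitative algorithm; none are stated for the qualitative read.
- It is tempting to say that the sensitivity threshold was moved to PPV by mistake. The match at 0.65 is suggestive, but the documents do not say where the PPV null came from.

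These points limit the consequences. They do not supply the missing PPV hypothesis, and they do not make a fixed NPV null of 0.7 informative when fewer than 30% respond.

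**Conclusion.** The point holds as a defect in secondary testing. The PPV null is unsupported by the sections cited for it, and the NPV null is borrowed from the baseline TUV_global hypothesis. At the ratio the SAP expects for week-24 ACR50, the NPV test credits an uninformative read in nearly every trial (above 99.9% for a coin flip, 94% if it predicts response in 80% of patients). A read at the design values passes PPV about 2% of the time (4.8% with 120 predicted responders fixed).

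These sizes rest on 100:500, one-sided 0.025 and the quantitative design values. One-sided 0.05 does not change the conclusion; a ratio of 3:1 or below does.

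The co-primary tests, and the baseline NPV test that follows them, do not use these p-values, so the trial's main conclusion is unaffected. The change is still worth making, because the NPV p-value as written can mislead and the remedy is already used in the same section for the quantitative algorithm.

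**What to change.** In SAP 4.2.3 and the shell for Tables 21-28:

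- Add sensitivity and specificity for the qualitative and qualitative-plus-quantitative reads, with exact confidence intervals, and test them against 0.65 and 0.80 as for the quantitative algorithm.
- Keep PPV, NPV and OA with exact intervals, and drop the p-values against fixed nulls.
- Correct the reference to sections 1.3 and 4.2.1 so that it points to hypotheses found there. State the sidedness, and name the combined read in the text as well as in the shell.

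The same 2 by 2 counts serve, so no new data are needed and neither the sample size nor the primary analysis changes. The cost is revised SAP wording and table shells, and the loss of the PPV and NPV p-values. The 0.65 and 0.80 nulls were set for the quantitative algorithm, so the SAP should say that they are adopted here to put the reads on a common scale.

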9.5.3.3 Analysis of Secondary Efficacy Variables

All RA quantitative assessment variables (CDAI, ACR Response Criteria component scores, DAS28 score, and HAQ-DI) will be summarized by computing the mean, standard deviation, number of observations, minimum, median, and maximum for the observed values at each time point and for the change from baseline for values collected after Day 0. The ACR Response Criteria will be summarized with a frequency table of the highest ACR Response level (None, ACR20, ACR50, ACR70) attained by that patient at that time point. That is, a patient who satisfies ACR50 also satisfies ACR20 but will not appear in the frequency count for ACR20.

Concordance of improvement classification for $\Delta TUV_{global[5w]}$ bucketing with clinical criteria (ACR Response, CDAI, DAS28, and HAQ-DI) will be analyzed as follows. Note that the concordance of $\Delta TUV_{global[5w]}$ bucketing with ACR50 is evaluated as co-primaries (sensitivity and specificity). For each of the RA improvement criteria, a cross-classification table will be provided. The sensitivity, specificity, PPV, NPV, and OA will be calculated and 95% exact (Clopper-Pearson) confidence intervals will be provided.

The Kendall rank correlation between $\Delta TUV_{global[5w]}$ with $\Delta CDAI_{12w}$ and $\Delta CDAI_{24w}$ will be computed and a 95% confidence interval for its value will be computed using Fisher's Z transformation. Similarly, the Kendall rank correlation between $\Delta TUV_{global[5w]}$ with changes from baseline in DAS28 and in each of the ACR Response Criteria components at weeks 12 and 24 will be computed and a 95% confidence interval for its value will be computed using

Fisher's Z-transformation. The marginal distributions of the variables will be characterized with the mean, standard deviation, and the number of data pairs.

Additional efficacy analyses may be described in the NAV3-33 Statistical Analysis Plan (SAP).

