1.3 Sample Size

NAV3-33 is sized with respect to achieving specified goals in the co-primary endpoints of sensitivity and specificity of $\Delta TUV_{global[5w]}$ with bucketing. Sensitivity and specificity require knowledge of the patient's clinical status at Week 24, and so hypothesis testing will be performed after classification. The value of $\Delta TUV_{global[5w]}$ necessary to predict response vs. non-response and the value of $TUV_{global[5w]}$ necessary to predict response vs. non-response and the value of TUV_{global[b]} at baseline necessary to predict non-response will be determined in advance. The classification procedure occurs in two stages, following the baseline image acquisition and (possibly) following the 5 week image acquisition and calculation of $\Delta TUV_{global[5w]}$. After the baseline imaging, patients whose TUV_{global[5w]} is available, patients whose TUV_{global[b]} is ≥ 5 and D% is $\leq -10\%$ are predicted to be responders. All other patients are predicted to be non-responders. The Week 24 ACR50 will be used as the primary determination of clinical response for the reference standard

The hypotheses for the co-primary endpoints to be tested are:

$$H_{O1}: \pi_{Sp} \le 0.8$$

 $H_{A1}: \pi_{Sp} > 0.8;$

And

 $H_{02}: \pi_{Se} \le 0.65$ $H_{A2}: \pi_{Se} > 0.65.$

In the above π_{Sp} represents the true specificity of the classification procedure and π_{Se} represents the true sensitivity of the classification procedure when used to predict the outcome of the anti-TNF α bDMARD inhibitor therapy at 24 weeks. An overall two-tailed Type I error rate of 0.05 (one-tailed 0.025) was used without adjusting for multiple endpoints, as both co-primary endpoints must be achieved in order to have a successful study. If the actual specificity is 0.92 and the actual sensitivity is 0.8, and if an exact binomial test is used to test the above hypotheses, a total of 98 clinical non-responders and 100 clinical responders are needed for 90% power of the individual tests. That is, a minimum of 198 total patients is needed. This applies to a single reader.

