2.7 Documentation and Other Considerations

The data analyses will be conducted using SAS[®] Software, version 9.4 or later.

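### The 95% CI for Kendall's tau is specified only as Fisher's Z, with no standard error suited to tau; the usual 1/(n-3) variance would make it about 1.3 to 1.5 times too wide

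*SAP*

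**What the plan says.** SAP 4.2.3 plans Kendall rank correlations of the week-5 change in TUV with the week-12 and week-24 changes in CDAI, DAS28 and each ACR component. For each it states that a "95% confidence interval for its value will be computed using" Fisher's Z-transformation. Protocol 9.5.3.3 has the same plan: it opens with "The Kendall rank correlation between" and says a "95% confidence interval for its value will be computed using Fisher's Z transformation". The protocol synopsis repeats it.

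The Kendall table shells in SAP Appendix B (Tables 29, 31 and 33, repeated for the PP population as Tables 30, 32 and 34) carry the footnote "Confidence limits calculated using Fisher's Z-transformation".

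None of these places gives a variance, a standard error, a tie adjustment or a resampling method. On software, SAP 2.7 says "The data analyses will be conducted using SAS", and it names no procedure or option for this interval.

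**The concern.** Fisher's transformation fixes the scale on which the interval is built. It does not fix the standard error. For a product-moment correlation the usual companion is SE = 1/sqrt(n-3). Kendall's tau has a much smaller sampling variance, so that standard error is too large for it. A programmer who follows the named method in its usual form, with nothing in either document pointing elsewhere, would produce limits labelled 95% whose real coverage is higher.

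These correlations serve several secondary objectives: association with composite scores and their components, association for specific anti-TNF agents, and use in monitoring therapy. Over-wide limits would make weak but real associations look compatible with no association. The loss is greatest where pairs are few. Tables 31-34 need week-12 or week-24 images, which exist only for the patients who reached those visits before Amendment 4 took effect (protocol synopsis, duration of treatment). Agent-specific correlations use only part of the sample.

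**Working it through.** **Stated figure.** The documents give no width or standard error for this interval, so there is nothing to reproduce.

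**Inputs.** The number of pairs is taken from SAP 1.3.
- Lower value 198 ("a minimum of 198 total patients is needed"). This is 98 non-responders plus 100 responders. Exact one-sided 0.025 binomial tests give power 0.908 and 0.913 for these two groups, in line with the stated 90%.
- Upper value 600 ("a total of 600 patients is needed to achieve the desired power"). Protocol 9.4 prints 654 in the matching sentence, but the width ratio hardly depends on n.

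**Step 1: formulas.** Interval = tanh(atanh(tau) ± 1.96 × SE).
- Usual Fisher SE: 1/sqrt(n-3).
- Fieller-Hartley-Pearson SE for tau: sqrt(0.437/(n-4)).
- Large-sample ratio: 1/sqrt(0.437) = 1.51.
- Cross-check: under independence without ties Var(tau) is about 4/(9n), so the ratio is 1/sqrt(4/9) = 1.50.

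**Step 2: example, n = 198, tau = 0.2.** atanh(0.2) = 0.2027.
- Usual SE: 1.96/sqrt(195) = 0.1404, limits 0.062 to 0.330, width 0.268.
- Tau SE: 1.96 × sqrt(0.437/194) = 0.0930, limits 0.109 to 0.287, width 0.178.
- Ratio 1.50.

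**Step 3: widths at other values.**

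| n | tau | width, 1/(n-3) | width, 0.437/(n-4) | ratio |
|---|---|---|---|---|
| 198 | 0 | 0.279 | 0.186 | 1.50 |
| 198 | 0.3 | 0.254 | 0.169 | 1.51 |
| 600 | 0 | 0.160 | 0.106 | 1.51 |
| 600 | 0.3 | 0.146 | 0.097 | 1.51 |

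For n = 100 to 672 and tau = 0 to 0.7 the ratio is 1.49 to 1.51.

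**Step 4: simulation.** n = 198 and 600, five strengths of association, 1,500 runs per setting. The second column is 1/sqrt(n-3) divided by the simulated SD of atanh(tau). Coverage is of the mean simulated tau. The distributions are assumptions.

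| Data | SE ratio | coverage, 1/(n-3) | coverage, 0.437/(n-4) |
|---|---|---|---|
| Bivariate normal, untied | 1.47-1.66 | 99.6-100% | 94.0-97.0% |
| Both variables rounded | 1.40-1.53 | 99.2-99.8% | 92.1-95.6% |
| One variable coarsely rounded | 1.33-1.50 | 98.5-99.7% | 91.5-94.8% |
| Heavy-tailed (t, 3 df) | 1.28-1.37 | 98.5-99.6% | 90.1-92.6% |

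Ties are to be expected here: joint counts are integers and the global scores move in steps of 0.5 (Protocol 8.3.5). In a further simulation at n = 60, 198 and 600, the 1/(n-3) interval covered 98.7-100%. The interval from the asymptotic standard error of tau-b covered 93-97% in every setting.

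**Step 5: where a reading would change.** The smallest observed tau whose interval excludes zero is tanh(1.96 × SE).
- n = 600: 0.080 with 1/(n-3), 0.053 with 0.437/(n-4).
- n = 198: 0.139 against 0.093.
- n = 50 (assumed, since the documents give no subset size): tanh(1.96/sqrt(47)) = 0.278 against tanh(1.96 × sqrt(0.437/46)) = 0.189.

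The chance that the interval excludes zero, for untied data, is 20% against 56% at n = 198 with true tau 0.1, and 20% against 55% at n = 50 with true tau 0.2. At n = 600 with true tau 0.2 it is about 100% either way.

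**The case against.** The strongest reply is that neither document writes 1/(n-3). Fisher's Z is a legitimate scale for tau if a standard error suited to tau goes with it. A reader might infer that the plan prescribes a wrong formula, but the text does not support that. What it contains is an unstated standard error, and the excess width depends on the programmer taking the usual default. This stands, and it limits the point to a gap in specification. It does not remove the point, because a pre-specified analysis should not leave the width open by a factor of up to about 1.5.

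Second, a flat factor of 1.5 describes only untied, roughly normal data. This also stands: with ties or heavy tails the range is about 1.3 to 1.5. In a deliberately severe case, with half of the values in each variable tied, simulation at n = 300 gave 1.18-1.26.

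Third, replacing the default with 0.437/(n-4) would swap a conservative error for an anti-conservative one. This stands for data of this kind, as step 4 shows; in the severe tie case coverage fell to 87-90%.

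Fourth, a reader might infer that the monitoring objective is undermined or that trial success is at risk. The documents do not support either. No hypothesis, p-value or alpha is attached to these correlations. Success rests on sensitivity and specificity, and then NPV, all by exact binomial methods. The estimates of tau do not change. At the planned sample sizes, only correlations in a narrow weak band would be read differently.

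**Conclusion.** The point holds as a missing specification. If the usual Fisher variance is used, limits labelled 95% are about 1.5 times too wide for untied, roughly normal data and about 1.3 to 1.5 times too wide with ties or heavy tails, with real coverage of about 99% or more (lowest 98.5% in the step 4 settings). The direction was the same in every setting tried.

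The consequence is limited. The error is conservative and touches only secondary descriptive output, and it affects interpretation mainly for weak correlations or small subsets. The co-primary and key secondary analyses are unaffected. The conclusion rests on two assumptions: that 1/(n-3) would be the default, because no other variance is named, and that the simulated distributions resemble the trial's data.

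**What to change.** In SAP 4.2.3, Protocol 9.5.3.3 (and the matching synopsis text) and the footnotes of Tables 29-34, name the standard error. Suitable wording: the 95% CI for Kendall's tau-b uses its tie-adjusted asymptotic standard error (ASE). If the Fisher Z scale is to be kept, the delta method gives tanh(atanh(tau) ± 1.96 × ASE/(1 - tau²)). A patient-level bootstrap is an acceptable alternative.

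State that 1/(n-3) is not used, and do not substitute 0.437/(n-4), given its under-coverage with ties or heavy tails.

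The cost is one sentence in each place and a small programming change, made before the analysis is run. It needs no new data and no change to design or sample size.
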